5.1 Primary endpoint

There is debate regarding utility of various surrogate markers of NAFLD in clinical trials²⁸. Consensus opinion is that histology-based outcomes should be reserved for longer trials because of risks of liver biopsy. ALT is a "reasonably likely to predict clinical outcome surrogate marker" frequently used in phase I and II trials of NAFLD because it reflects inflammation in the liver. CK-18 detects hepatocellular death, however it is less useful in children²⁴. Finally, while MRI is highly accurate for measuring steatosis and has been used extensively by our group^{9, 29-31}, change in steatosis is less predictive of longer term clinical benefit. Thus, we have selected the percent change in ALT as the primary efficacy related outcome. The amount of change in ALT that meets the surrogate marker standard is debated and depends on 1) the baseline ALT, 2) the length of time of treatment and 3) the mechanism of the product/drug. In this study, all participants will have at least ALT $\ge 2 \times ULN$ at screening (girls ≥ 46 , boys ≥ 54). Furthermore, a clinically relevant outcome would be at least a 25% reduction in ALT from baseline to week 12. Because this is a proof of concept study, if the primary outcome is not met but other important secondary markers are

met, this will support the design of future studies. In addition, other potential primary outcomes are being tested as secondary outcomes in this proof of concept study.

5.2 Secondary Endpoints

Secondary efficacy-related outcomes will include change in: GGT, fasting glucose and insulin, total body insulin sensitivity (OGTT), BMI z-score, waist circumference, and quality of life. Safety-related outcomes will include: sex hormones, proportion of participants with nausea, emesis, diarrhea, and any other adverse event, PROMIS, body fat by MRI, hepatic fat by MRI, and change in metabolic state.

5.3 Power Analysis:

A typical group of patients with NAFLD have a mean ALT level of $130 \pm 63 \text{ U/L}^{10}$. In the TONIC treatment study of children with NAFLD, there was a -20 ± 10 U/L and -30 ± 8 U/L change (average of 15% – 23% change) in ALT in treatment groups respectively and no change in ALT with placebo at 12 weeks⁶. A sample size of 11 participant per group is required to achieve a least 90% power to detect a 15% point difference in the average % change in ALT from baseline to week 12 between the two groups. Sample size was calculated assuming common standard deviation of 10% using a two-sided Mann-Whitney tests with a 0.05 significance level.

5.4 Statistical Analysis:

Primary Outcome Analysis:

Change in ALT from baseline to week 12 will be converted to a % change from baseline to account for the wide range of ALT values expected at baseline. A Mann-Whitney U test will be used to compare the percentage change in ALT among the two intervention groups. Data will be described as mean or median percent change, as appropriate.

General Statistical Considerations:

Analysis of primary and secondary outcomes will be performed using an intention to treat analysis. Descriptive variables of the cohort and subgroups will be analyzed using means and standard deviations, medians and ranges, or counts and percentages, as appropriate. For secondary measures, absolute change over time will be compared using mixed models or analysis of covariance. We will test the data to evaluate underlying model assumptions (i.e., normality, homoscedasticity). If these assumptions are not met, then we will attempt to transform the data. Standard transformations of the response variable such as the log, square root and Box-Cox transformations will be examined. If data transformation is inadequate to meet the analysis assumptions, then rank transformation of the data will be performed and the rank transformed response variables will be analyzed and reported. In situations where covariates could potentially have an effect on the response variable, we will add covariates to adjust for subgroup effects. Underlying model assumptions will be tested (such as homogeneity of slopes across exposure groups). Standard regression criteria will be used to assess appropriateness of including particular covariates. Collinearities will be reduced in multivariable modeling through the careful initial assessment of correlations and the avoidance of redundancies in candidate covariates.

With multiple follow-ups, longitudinal data will be available, and these repeated measures are likely to be correlated (i.e., weight, PROMIS measures, BMI-score, etc.). The analysis of repeated measures data is needed that properly accounts for the correlation between multiple observations from the same participant. Mixed effects models, accounting for the longitudinal measures, will be summarized with adjusted means and 95% confidence intervals for continuous outcomes. For categorical outcomes, we will apply generalized linear mixed models with appropriate distribution and link functions. In these models, the statistical test for interaction between time on study and intervention group will be the primary overall hypothesis to test to determine whether an outcomes in the two study groups changed in significantly different ways during follow-up (i.e., different temporal patterns over time). For significant interactions, post-hoc tests will be used to compare differences in the least square means at each time point in each intervention arm. All statistical tests will be two-sided and unadjusted for multiple comparisons due to the pilot nature of this trial.

Missing Data: A potential problem in any of the proposed analyses is missing data, which can cause the usual statistical analysis of complete available data to be subject to bias. Every effort will be made to minimize missing data on outcomes and covariates, and we will encourage patients that drop out of a study to return for final follow-up testing even if they missed previous scheduled evaluations.

Sensitivity Analysis: A sensitivity analysis will be performed by examining the effect of compliance (i.e., number of doses taken) on the primary and secondary endpoints.

5.5 Data Storage & Sharing:

Hard copy data will be entered by the study coordinators. All data will be stored in a REDCap database. Only study personnel (PI, Co-I's study coordinators, research assistants etc.) will have access to identifiable data. Data will be de-identified before analysis. Data will be stored in locked research material cabinets and in password-secured on the Emory network.

De-identified data will be shared with Immuron Ltd. and a sub-set of de-identified data will further be shared with Advanced MR Analytics AB (AMRA) who is providing imaging analysis services for the study.

5.6. Sample storage:

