	improvement in TG/HDL ratio, improvement in insulin resistance, and >10%		
	improvement in ALT		
Study Duration (per	Up to 19 weeks total		
participant):	• Up to 6 weeks screening		
	12 week treatment		
Study Duration (calendar	• Study start-up: 0 – 4 months		
time):	Recruitment phase: 5 -14 months		
	Follow-up phase: 15 - 18 months		
Math Cale a duile :	Analysis and reporting: 18 - 24 months		
Visit Schedule:	Screening Visit		
	Baseline visit		
	Follow up visits		
Ctatistical Analysis	• Week 6 and Week 12 visits		
Statistical Analysis:	Descriptive variables of the cohort and subgroups will be analyzed using means and standard deviations or medians and ranges, as appropriate. Percent change in		
	primary and secondary outcomes will be compared using two sample t-test or		
	Mann-Whitney test. Absolute change over time will be compared using mixed		
	model or analysis of covariance.		
Sample Size:	A sample size of 11 participant per group is required to achieve a least 90% power		
Sample Size.	to detect a 15% point difference in the average % change in ALT from baseline to		
	week 12 between the two groups. Sample size was calculated assuming common		
	standard deviation of 10% using a two-sided Mann-Whitney tests with a 0.05		
	significance level. We will include 20 participants per group to allow for drop out,		
	intra-individual variability and multiple hypothesis testing.		
Safety Monitoring:	A DSMB will monitor the data for safety and efficacy for outcomes such as nausea,		
earcey monitoring.	abdominal pain, flatus, diarrhea, pregnancy, hepatotoxicity and any other outcomes		
	or events identified as safety related.		

Table of Contents

1.1 Primary Objectives71.2 Secondary Objectives72. Background & Significance73. Study Design113.1 Design Overview113.2 Inclusion Criteria113.3 Exclusion Criteria113.4 Rescreening123.5 Treatment Groups123.6 IMM-124E Administration123.7 Recruitment and Retention133.8 Sources and Materials133.9 Potential Risks133.10 Protection Against Risks143.11 Potential Benefits153.12 Data and Safety Monitoring164. Study Plan16
2. Background & Significance.73. Study Design.113.1 Design Overview.113.2 Inclusion Criteria.113.3 Exclusion Criteria.113.4 Rescreening.123.5 Treatment Groups.123.6 IMM-124E Administration.123.7 Recruitment and Retention.133.8 Sources and Materials.133.9 Potential Risks.133.10 Protection Against Risks.143.11 Potential Benefits.153.12 Data and Safety Monitoring.16

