3.4 Rescreening

If a potential participant fails screening due to a changeable criteria such as acute illness, use of a supplement or anti-oxidant, and ALT < $2 \times ULN$, the participant may rescreen a second time if they desire to after a reasonable amount of time has passed and if the investigator thinks the participant is likely to qualify the second time.

3.5 Treatment Groups:

Characteristics: 40 children age 6-19 years from any ethnic and racial categories will be included. Males and females will be recruited equally, however because of the increased prevalence of NAFLD in adolescent boys compared to girls, we may enroll more boys. In order for 40 children to complete the protocol, we will over-enroll at baseline by approximately 5 additional participants to allow for dropout.

NAFLD Patient Eligibility: Children ages 6-19 will be included because NAFLD typically presents around age 10, although sometimes at a young age. Young adults, age >19 years, will not be included because their travel for school and work makes participation more difficult. For NAFLD, each patient must meet the typical criteria for diagnosis including typical clinical and laboratory changes of NAFLD and liver biopsy or MRI consistent with NAFLD. If the subject only has had an ultrasound they may have their baseline MRI conducted up to 2 weeks prior to confirm the diagnosis. Subjects with 5% or more liver fat on their MRI will meet entry criteria and can proceed with the study. Other chronic liver disease must have been ruled out using a serologic work-up.

3.6 IMM-124-E Administration:

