- Urine pregnancy test for females of childbearing potential
- Blood spot collection
- MRI (Brief scan for full body and liver fat assessment)

• Optional Sub-study: Accelerometer data collection for 1 week

4.2 Randomization Procedures:

After consent and eligibility for the trial is confirmed, participants will be randomly assigned to either IMM-124E or placebo. The randomization will be assigned by the research pharmacist and will be blocked by age group (6-12 years versus 13-19 years) to ensure balanced groups. The investigators, lab personnel, research coordinators and participants will be blinded to the assignment. The research pharmacy will dispense the similarly appearing IMM-124E and placebo at baseline and again at Week 6.

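### The primary Mann-Whitney on percent change in ALT ignores Week 0 ALT and the age groups used to block randomisation: it is valid, but a cheap gain in precision is left unspecified

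*Combined protocol and SAP*

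**What the plan says.** Section 5.4 (Primary Outcome Analysis) forms the endpoint from Week 0 and Week 12 ALT, "converted to a % change from baseline to account for the wide range of ALT values expected at baseline", and then states: "A Mann-Whitney U test will be used to compare the percentage change in ALT among the two intervention groups". It names no covariate or stratum. The Synopsis offers a two-sample t-test as an alternative for percent change, which is equally unadjusted.

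Section 4.2 says that randomisation "will be blocked by age group (6-12 years versus 13-19 years) to ensure balanced groups". No analysis section refers to those age groups again.

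Adjusted models are placed elsewhere. Section 5.4 (General Statistical Considerations) says: "For secondary measures, absolute change over time will be compared using mixed models or analysis of covariance". It adds: "In situations where covariates could potentially have an effect on the response variable, we will add covariates to adjust for subgroup effects". That sentence names no covariate and is not tied to the primary test. The 95% intervals promised in 5.4 belong to the mixed models. Mean change in ALT is listed as a secondary endpoint (Section 1.2).

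On variability, Section 5.3 states: "Sample size was calculated assuming common standard deviation of 10" per cent. The Synopsis raises 11 per group to 20 to cover dropout, "intra-individual variability and multiple hypothesis testing".

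**The concern.** Dividing by the Week 0 value does not remove dependence on it. When the within-child correlation r of log ALT is below 1, a child with a high Week 0 value tends to show a larger percent fall in either arm. In simulation the Spearman correlation between Week 0 ALT and percent change is -0.49, -0.39, -0.32 and -0.22 at r = 0.5, 0.7, 0.8 and 0.9. That predictable variation stays as noise in the planned test. Likewise, if a blocking factor predicts outcome, blocking reduces the true variance of the treatment comparison, but a test that ignores the factor does not use the reduction.

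At stake is precision, not validity. The primary endpoint also has a test and a descriptive summary but no planned interval for the treatment difference. Section 2 says that the study is meant to inform the design of a larger trial, and an interval is what that design needs.

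**Working it through.** **Inputs from the documents.** Section 5.3: ALT 130 ± 63 U/L, difference 15 points, SD 10 points, two-sided 0.05, 11 per group for 90% power. Synopsis: 20 per group. Section 5.1: 25% reduction called clinically relevant. Section 3.2: screening cut-offs 46 (girls) and 54 (boys).

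**Assumptions (not in the documents).** r from 0.5 to 0.976, equal between visits; lognormal ALT with equal log variance at each visit; 40% girls; age strata of 8 and 12 per arm; noise shape; size of any age effect.

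**1. The plan's figure.** n = 2(1.960 + 1.282)² × (10/15)² = 9.34 per group. Dividing by the Mann-Whitney efficiency 3/π gives 9.78. Simulated Mann-Whitney power is 0.853 at 10 and 0.901 at 11 per group, so 11 is reproduced. At 20 per group, power on the same inputs is about 99%.

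**2. The r implied by an SD of 10.** Log-scale SD s = √ln(1 + (63/130)²) = 0.459, so s² = 0.211. The log change has variance 2s²(1 − r). Setting this to 0.10² gives r = 1 − 0.01/(2 × 0.211) = 0.976. For other r, with v = 2s²(1 − r), the SD of percent change is 100 × √(e^v − 1) × e^(v/2).

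**3. Large-sample gain from Week 0 ALT.** Log change has variance 2s²(1 − r); the residual after regression on Week 0 has s²(1 − r²). The ratio is (1 + r)/2.

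**4. Power.** 20 per arm, 20,000 simulated trials per setting, normal noise, no age effect. The adjusted rank test regresses log Week 12 ALT on log Week 0 ALT and age group, without arm, and compares the residuals by Mann-Whitney.

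| r | SD of % change | (1 + r)/2 | 25% reduction, planned / adjusted (%) | 15% reduction, planned / adjusted (%) |
|---|---|---|---|---|
| 0.5 | 54 | 0.75 | 47 / 58 | 19 / 24 |
| 0.7 | 39 | 0.85 | 68 / 75 | 28 / 32 |
| 0.8 | 31 | 0.90 | 84 / 88 | 38 / 42 |
| 0.9 | 21 | 0.95 | 98.8 / 99.0 | 66 / 68 |
| 0.976 | 10 | 0.99 | 100 / 100 | 99.8 / 99.8 |

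Type I error is 4.6 to 5.2% for the planned test and 4.8 to 5.6% for the adjusted one.

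**5. Age group.** Suppose ALT in one age group falls 20% more in both arms. The planned test's type I error drops to 4.2, 3.7, 3.4 and 2.6% at r = 0.5, 0.7, 0.8 and 0.9. Its power for a 25% reduction falls to 44, 64, 81 and 97.2%, that is 3, 4, 3 and 1.6 points below the table. The adjusted test keeps 58, 75, 88 and 98.9%. With a 10% age effect, the planned type I error is 4.1 to 4.8%. A Mann-Whitney stratified by age (van Elteren) at r = 0.8 with the 20% effect restores type I error to 4.9% and lifts power from about 80 to 83%.

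**6. Heavy tails, no age effect.** With t(3) noise, power for a 25% reduction, planned / adjusted rank, is 66/72, 85/87, 95.1/94.8 and 99.9/99.7 at r = 0.5, 0.7, 0.8 and 0.9. For a 15% reduction at r = 0.9 it is 84.2/82.5, and 82.8/81.0 when 10% of values have a fourfold SD. ANCOVA on log ALT loses more: 90% against 95% for the planned test (25% reduction, r = 0.8, t(3)).

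**7. Interval.** ANCOVA 95% interval coverage is 94.7 to 95.7%. For a true 25% reduction with normal noise, the median interval is -37 to -11% at r = 0.8 and -34 to -15% at r = 0.9.

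**The case against.** The strongest reply is that nothing is wrong on the plan's own inputs. Power at SD 10 is about 99% with or without adjustment, a rank test is a defensible robust choice, and every gain rests on an assumed r or age effect. The planned test at 20 per arm keeps about 90% power up to an SD of about 14 for 15 points, or about 23 for 25 points. At SD 39 to 54 the larger problem would be sample size: power for a 15% reduction is only 24 to 32% even after adjustment. All of this stands.

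A reader might infer that the documents themselves show an SD above 10. They do not. The Synopsis gives intra-individual variability as one of three reasons for 20 per group, which is provision for variability and not an estimate of it. Section 3.4 covers a candidate who "fails screening due to a changeable criteria such as acute illness", and later in that sentence also lists ALT below 2 × ULN, but gives no SD.

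A reader might also infer that the adjusted rank test leaves the declared endpoint untouched. The residuals of log Week 12 ALT and of log(1 + percent change/100) on the same covariates are identical, but ranking them tests a conditional shift in log ratio, not percent change itself.

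Finally, the secondary mean-change endpoint already gets ANCOVA or a mixed model. That answers part of the point. It still names neither Week 0 ALT nor age group, and it gives no interval for the percent comparison.

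**Conclusion.** The point holds as a modest, optional improvement in precision. It would be wrong to read it as bias or inflated type I error: where age is prognostic, the planned test errs towards conservatism. Nor do the documents show that the trial is underpowered for want of covariates, or that the primary test must be replaced.

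Under normal noise, a useful gain from Week 0 ALT (4 to 11 points for a 25% reduction) needs an SD of percent change about three or more times the plan's 10. At SD 21 it is 0 to 2 points, and at SD 10 nil. The gain from age group is separate. It depends wholly on how strongly age predicts ALT change, which the documents do not give, and may be nil. Heavy-tailed noise with stable ALT turns the baseline gain into a loss of up to about 2 points. What remains whatever the value of r is that the primary comparison has no planned interval and the blocking factor is absent from the analysis.

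**What to change.** Before unblinding, add to Section 5.4 an ALT comparison adjusted for Week 0 ALT and age group:

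- **Estimate:** ANCOVA of log Week 12 ALT on arm, log Week 0 ALT and age group, reported as the adjusted percent difference versus placebo with a 95% confidence interval.
- **Robust p-value:** Mann-Whitney on the covariate-adjusted residuals, fitted without arm.

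Then choose one of two arrangements:

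1. Make the adjusted rank test primary, with the planned Mann-Whitney on percent change as a sensitivity analysis.
2. Keep percent change as the primary test, stratify it by age group (van Elteren), and name the adjusted analysis as the key supportive one. This suits a sponsor who puts robustness first.

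Either way, state in advance which p-value governs if the analyses disagree. Say also that the adjusted analysis estimates a conditional ratio, not the percentage-point difference used in Section 5.3.

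Cost: no new data or visits, two covariate degrees of freedom, a model assumption for the interval, and up to about 2 points of power for the adjusted rank test under heavy tails when ALT is stable.

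### Age group is used to block the randomisation but appears in no analysis, the secondary models name no baseline covariate, and other covariates are left to an unspecified selection rule

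*Combined protocol and SAP*

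**What the plan says.** Section 4.2 (Randomization Procedures) says that the assignment "will be blocked by age group (6-12 years versus 13-19 years) to ensure balanced groups". Section 5 does not mention age group again, either as a stratum or as a covariate.

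For the primary outcome, section 5.4 (Primary Outcome Analysis) names one unadjusted Mann-Whitney U test on percent change in ALT. The sample size in section 5.3 rests on the same test: "Sample size was calculated assuming common standard deviation of 10% using a two-sided Mann-Whitney tests with a 0.05 significance level". The synopsis (Statistical Analysis) is looser. It says that percent change in "primary and secondary outcomes will be compared using two sample t-test or" Mann-Whitney, and gives no rule for choosing.

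For secondary measures, section 5.4 (General Statistical Considerations) offers mixed models or analysis of covariance for absolute change. It then says: "If these assumptions are not met, then we will attempt to transform the data", listing log, square root, Box-Cox and finally ranks. Covariates that might affect the response may be added, and "Standard regression criteria will be used to assess appropriateness of including particular covariates". The plan gives no candidate list, entry threshold or lock point, and it does not say whether treatment arm is in the model during selection. Nowhere is the baseline value of an outcome named as a covariate.

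**The concern.** A factor that constrains the randomisation belongs in the analysis. Blocking makes the arms more alike on age than chance would. An analysis that ignores age still counts the age-related spread as noise, so its standard error is too large. If age is prognostic, the trial forgoes the precision that blocking was meant to buy. The same applies to baseline values, which are measured and are usually the strongest predictor of the week-12 value.

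The open covariate rule raises a separate, smaller issue. If covariates are selected on outcome data with arm in the model, the treatment p-value is no longer exact. This bears on the secondary outcomes, and they matter here: section 5.1 says that favourable secondary markers would support future studies even if the primary outcome is missed, and section 5.4 leaves all tests unadjusted for multiplicity.

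**Working it through.** **The plan's own figure.** Section 5.3 states: "A sample size of 11 participant per group is required to achieve a least 90% power to detect a 15% point difference". With a 15-point difference and SD 10 (1.5 SD), a noncentral t calculation gives 91.7% power at 11 per group. A simulated exact Mann-Whitney test on normal data gives 89.6% at 11 and 91.9% at 12. The stated 11 is reproduced within tolerance and does not depend on this point. The calculations below use the 20 per arm in the synopsis.

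**Omitting the age stratum.** Inputs: n = 20 per arm; two equal age groups balanced across arms (assumed); treatment effect d = 0.9 SD (assumed); age effect g in SD units (assumed).

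- The treatment estimate has standard error √(2/n) SD, so its expected standardised value is d·√(n/2) = 0.9 × √10 = 2.846.
- With the stratum in the model, the critical value is t(37) = 2.026. Power ≈ Φ(2.846 − 2.026) = 79%.
- Without it, the residual variance grows by the factor 1 + g²/4, so the effective critical value is 2.024 × √(1 + g²/4). Type I error below is the two-sided t(38) tail beyond that value.

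| Age effect g | Variance factor | Effective critical value | Type I error | Power |
|---|---|---|---|---|
| 0 | 1.00 | 2.024 | 5.0% | 79% |
| 0.5 | 1.0625 | 2.086 | 4.4% | 78% |
| 0.8 | 1.16 | 2.180 | 3.6% | 75% |
| 1.0 | 1.25 | 2.263 | 2.9% | 72% |

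Simulation of the same settings gives power of 79, 78, 74 and 71% without the stratum against 79-80% with it, and type I error of 3.0% at g = 1.0. The unadjusted Mann-Whitney test gives 71% and 68% power at g = 0.8 and 1.0.

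**Omitting baseline.** For an absolute change, the ratio of ANCOVA variance to change-score variance is (1 − ρ²)/(2 − 2ρ) = (1 + ρ)/2, where ρ is the baseline to week-12 correlation. This is 0.75, 0.85 and 0.95 at ρ = 0.5, 0.7 and 0.9 (assumed).

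As an indication for ALT, take a log-normal baseline from the 130 ± 63 U/L in section 5.3 (log SD 0.459) and the 25% reduction that section 5.1 calls clinically relevant. Simulated power at 20 per arm, Mann-Whitney on percent change against ANCOVA on log ALT, is 47% versus 60% at ρ = 0.5, 67% versus 75% at 0.7, 85% versus 89% at 0.8 and 98.7% versus 99.2% at 0.9. Part of this gain comes from the scale and the parametric test, so not all of it is due to baseline.

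**Selecting covariates (secondary models).** Simulated type I error at 20 per arm, all candidates unrelated to the outcome:

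- Forward AIC with arm in the model: 6.4%, 7.4% and 8.7% with 4, 6 and 10 candidates in one set of runs; 6.2-8.3% over the same span in another. The Monte Carlo standard error for 3,000 runs near 8% is √(0.08 × 0.92/3000) = 0.5 points, so the sets agree.
- Forward entry at p < 0.05 with arm in the model: 5.7%, 6.3% and 6.7%.
- Selection with arm left out: 4.4-5.5% across all runs, essentially nominal.
- Covariates fixed in advance: 4.5-5.2%.

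**The case against.** The strongest reply is that the primary analysis is already fixed and valid. Section 5.4 names one rank test, section 5.3 sizes the trial on it, and the covariate and transformation text follows a sentence confined to secondary measures. That stands. A reader of the synopsis might infer that the primary test will be chosen after the data are seen. The documents do not support this: no rule for picking a test on results is stated anywhere, and the two passages simply differ and need reconciling. Likewise, the transformation sequence is triggered by assumption checks, not by the treatment p-value. A choice between t-test and Mann-Whitney by a normality pre-test gives a simulated type I error of 5.0-5.5%.

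Baseline is also not wholly absent. Percent change uses it, and ANCOVA for absolute change commonly adjusts for it, although the plan does not say so.

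The power loss depends on an age effect that the documents do not give; if age is not prognostic, nothing is lost. Under the plan's own 1.5 SD effect the primary test has power to spare: the expected standardised value is 1.5 × √10 = 4.743, so even at g = 1.0 power is Φ(4.743 − 2.263) = 99.3%, against Φ(4.743 − 2.026) = 99.7% with the stratum. The loss matters only where the true standardised effect is smaller, which is possible for ALT and is not ruled out for any secondary outcome.

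Finally, this is a pilot that declares its tests unadjusted. That lowers the stakes, but it is no reason to leave out a design factor that costs nothing to include.

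**Conclusion.** The point holds as a matter of precision and pre-specification and should be fixed. Age group is a design factor missing from every stated analysis, and no secondary model states a baseline covariate. With a 0.9 SD treatment effect at 20 per arm, leaving out the stratum costs nothing if age is not prognostic, about 2 points of power at an age effect of 0.5 SD and about 5-8 points at 0.8-1.0 SD.

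A reader might infer that the plan as a whole inflates false positives. It does not. Omitting the stratum lowers type I error, and the primary test has no covariate step. Inflation is possible for secondary outcomes only, to about 6-8% (8.7% at the highest), and only if selection is stepwise with arm in the model and there are some 4-10 null candidates. The plan neither describes nor excludes that procedure. Arm-blind selection stays near 5%.

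The treatment effect, age effect, baseline correlation and number of candidates are assumptions, not figures from the documents.

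**What to change.** In section 5.4 (General Statistical Considerations), state that every mixed model or ANCOVA includes arm, the baseline value of the outcome and age stratum (6-12 versus 13-19 years). Where a mixed model treats the baseline visit as one of the repeated responses, say how baseline is handled, so that it does not enter twice. State that any further covariate or transformation is fixed before unblinding and is not selected on outcome data by arm. No blanket log-transformation rule is needed; change scores can be negative, so it would not suit them.

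For the primary outcome, use an age-stratified rank test (van Elteren) or a rank ANCOVA with age group and baseline ALT. The first uses the stratum only; the second also uses baseline. Name that one test identically in the synopsis and in section 5.4 (Primary Outcome Analysis).

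The cost is a wording amendment made before unblinding, with no new data or visits. It gives up one or two degrees of freedom (one moves the critical value from 2.024 to 2.026) and some post hoc flexibility. The planned size can stay: "We will include 20 participants per group to allow for drop out" in the synopsis already exceeds the 11 per group required.
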